## **2. Secondary End Points:**

To compare the side-effects, including weight gain, irregular vaginal bleeding, breast pain, appetite changes, nausea, vomiting, rash, jaundice, thromboembolism, hypertension, liver dysfunction, kidney dysfunction, glucose intolerance, and diabetes.

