### **I. Objectives and Introduction:**

In recent years, the number of young patients having atypical endometrial hyperplasia (EAH) and early endometrial cancer (EC) has been gradually increasing. EAH is a precancerous stage of EC, and the risk of developing EC from EAH is the highest (8%~30%). [1, 2] Women who and EC and are younger than 40 years of age account for 2% to 14% of all cases, among whom 70% are nulliparous. [2-5] These women are generally reluctant to undergo a total hysterectomy that would result in loss of fertility; instead, they prefer conservative treatment of EC and EAH.

The conservative treatment for young women with EC and EAH who desire to conceive has remained challenging. Some reports have revealed that oral highly active progestogens are effective as a conservative treatment option. [2] However, traditional treatments as such often have many and severe side-effects and contraindications including thromboembolism and hypertension, and complications including obesity, ovarian dysfunction such as polycystic ovary (PCO) syndrome, and fasting hyperglycemia. [6] These side-effects and contraindications often lead to withdrawal from therapy. Therefore, a new conservative treatment that is largely effective and widely applicable and has relatively mild side effects, is urgent needed.

On the one hand, levonorgestrel-releasing intrauterine system (LNG-IUS) has protects endometria and inhibits its hyperplasia; and on the other hand, it elevates local drug concentration with fewer and milder side-effects and contraindications, more convenient administration, and better effects than oral progestogens in theory. The use of LNG-IUS for the fertility-preserving treatment of EC and EAH has been proposed in many guidelines,[3, 5, 7-12] in which LNG-IUS was suggested as first-line medicine treatment for EAH by RCOG-BSGE. [1] Nevertheless, no appropriately designed randomized controlled trial (RCT) has been identified that investigates the optimal dosage, duration of treatment, lesion regression, and pregnancy rate after therapy in young women with EC and EAH, with regard to the use of LNG-IUS in particular. Therefore, we conducted the current prospective phase II study on fertility-preserving treatment of EC and EAH.

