**2.3 Conditions for Withdrawal from the Treatment (meeting any one of the following conditions)**

- (1) The participants volunteer to withdraw from the trial;
- (2) If the participants have PD on the histologic diagnosis; if the participants have PR and NC after 6 to 9 months of progestogen-based therapy; and if the participants have recurrence of disease while preparing for or during pregnancy;
- (3) If the participants cannot tolerate adverse drug reaction and are judged unfit for medical treatment by the clinician-in-charge.

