#### **3. Statistics:**

SPSS software will be used for statistical analysis. Survival analysis is used for primary end points and chi-square test for secondary end points.

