## **V. Research Status and Development Trend**

Endometrial carcinoma (EC) is the most common gynecology cancer worldwide, and is usually characterized by well-differentiated (grade 1 [G1]) and early stage (according to International Federation of Obstetrics and Gynecology [FIGO] staging system--stage IA), which contributed to a very high cure rate with standard treatment.[14, 15] Atypical endometrial hyperplasia (EAH) suggests a preliminary state with progression to EC, and tends to occur in young women. [1, 6-8] For these young patients, conventional treatment using hysterectomy affects their quality of life immensely because it deprives them of any chance to bear a child. If the patients have a strong wish to preserve their fertility, the fertility-preserving treatment can be considered. In China, as lifestyle and diet both change, the incidence of EC has been increasing very rapidly,[5, 14] and the need for fertility-preserving treatment is also on the rise.

The efficacy and safety of oral progestogens as fertility-preserving therapy in patients with EAH and EC has been reported in many studies. For instance, the first report was conducted by Kelley and Baker in 1961[16]. Oral progestogens function by inhibiting the estrogen receptor, leading to a decrease in endometrial cell mitosis, promotion of apoptosis, and production of secretory endometrium[17]. However, the highly active progestogens often have many and severe side-effects like gastrointestinal reaction, insomnia, nervousness, dizziness, coagulation, liver and

kidney dysfunction, and weight gain etc. In addition, these patients always have complications such as obesity, hypertension, and impaired glucose metabolism, which often make the patients withdraw from therapy. Therefore, an effective and safe conservative treatment is urgently needed for young patients having EAH and EC who wish to preserve their fertility but cannot tolerate the highly active progestogen treatment. It has become increasingly important and necessary to find a safe and effective fertility-preserving treatment with better tolerability, and fewer and milder side effects.

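### Milder side effects and side-effect withdrawals are part of the rationale, but the plan has no severity grade and no analysis of treatment stops

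*Combined protocol and SAP*

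**What the plan says.** All references are to the combined protocol and SAP.

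- **Rationale.** Section I says of oral progestogens: "These side-effects and contraindications often lead to withdrawal from therapy". It asks for "a new conservative treatment that is largely effective and widely applicable and has relatively mild side effects". Section V repeats the need for a "safe and effective fertility-preserving treatment with better tolerability, and fewer and milder side effects". Section I also expects LNG-IUS to offer "more convenient administration, and better effects than oral progestogens in theory", so tolerability is one strand of the case and efficacy is another.
- **Secondary end point (I.2).** "To compare the side-effects, including weight gain, irregular vaginal bleeding, breast pain, appetite changes, nausea, vomiting, rash, jaundice, thromboembolism", followed by hypertension, liver dysfunction, kidney dysfunction, glucose intolerance and diabetes: 14 named items. No grade, threshold or measure of discontinuation is given.
- **Analysis (III.3).** The whole provision is "chi-square test for secondary end points".
- **Stopping for side effects (II.2.3).** Condition (3) is "If the participants cannot tolerate adverse drug reaction and are judged unfit for medical treatment by the clinician-in-charge". Condition (1) is voluntary withdrawal. Neither appears among the end points.
- **Liver-function rule (II.3.1 comment 5; II.3.2 comment 8).** In the oral-progestogen groups only, continuing treatment depends on normal monthly liver tests.
- **Data collection (Tables 1 and 2).** Adverse events are checked at treatment start and every month to month 9.

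**The concern.** The rationale makes three tolerability statements: side effects should be fewer, they should be milder, and on existing treatment they contribute to women leaving therapy. The planned comparison matches only the first. Take an item such as nausea. If it is about as common in both arms but mostly severe in one and mostly mild in the other, a comparison of frequency finds nothing, although the difference is of the kind the rationale describes. If more women in one arm give up treatment because of side effects, no planned table or test reports it.

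Severity that is not recorded at the visit is hard to recover later, so the gap is best closed before data are collected. Stops can be counted afterwards from the withdrawal conditions. Without a prior definition, though, the choice of which stops to count would be made with the results in view.

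**Working it through.** **1. Rationale against planned analysis**

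| Statement in the rationale | Data in the plan | Planned analysis |
|---|---|---|
| Fewer side effects | Listed side effects; monthly adverse-event checks | Chi-square test (III.3) |
| Milder side effects | No grade or scale defined | None |
| Side effects leading to withdrawal | Conditions 2.3(1) and 2.3(3); liver-function rule | None |

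**2. What a frequency comparison misses (assumed rates)**

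The plan gives no side-effect or stopping rate, so there is no figure of its own to reproduce and every rate below is an assumption. Exact power for the uncorrected Pearson chi-square, two-sided 0.05, with n per arm and a and b women with the event:

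X² = 2n(a − b)² / [(a + b)(2n − a − b)]

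Power = sum over all (a, b) with X² > 3.841 of Bin(a; n, p1) × Bin(b; n, p2)

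Suppose 70% of each arm has a given side effect, but it is severe in 40% v 10%. With n = 20:

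- any occurrence, 70% v 70%: rejection probability 0.05, which is chance level;
- severe occurrence, 40% v 10%: power 0.62 (0.89 with n = 38).

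**3. Power for stopping because of side effects**

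III.1 gives 18 per group for EC and 20 per group for EAH, both without contraindications. Only these two cells contain an MPA 500 mg arm and an LNG-IUS-alone arm. Pooled, that is 18 + 20 = 38 per arm.

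| Assumed stopping rates | 18 v 18 | 20 v 20 | 38 v 38 |
|---|---|---|---|
| 15% v 5% | 0.13 | 0.15 | 0.33 |
| 20% v 5% | 0.25 | 0.29 | 0.55 |
| 25% v 5% | 0.39 | 0.44 | 0.74 |
| 30% v 5% | 0.53 | 0.59 | 0.87 |

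The pooled column is computed without stratification.

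**4. Precision at 25% v 5%**

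Approximate 95% half-width = 1.96 × √[(0.25 × 0.75 + 0.05 × 0.95)/n] = 1.96 × √(0.235/n).

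- n = 20: 1.96 × 0.108 = 0.21, so a difference of 20 points has an interval of about −1 to 41.
- n = 38: 1.96 × 0.079 = 0.15, so about 5 to 35.

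**5. Multiplicity**

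Fourteen tests at 0.05 have a chance of at least one false positive of 1 − 0.95¹⁴ = 0.51 if independent and all nulls are true. The plan makes no adjustment, so further comparisons should be labelled supportive.

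**The case against.** Several points on the other side stand.

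- **Efficacy is the objective.** Section I states the objective as therapeutic effect, pregnancy and birth. A reader might infer that the trial was built to find a tolerability advantage. The documents do not support that; tolerability is part of the reason for it.
- **The plan does test something relevant.** A reader might infer that the trial can show nothing about tolerability. That goes too far: comparing frequencies addresses fewer events, and the list already separates minor items (appetite changes, breast pain) from serious ones (thromboembolism, jaundice). Nausea and vomiting are separate items, so severity is masked only within an item.
- **A yes/no rule is not stated.** It is the natural reading of an ungraded list with a chi-square test, but the test could take graded categories had any been defined. The fault is under-specification.
- **The withdrawal claim is mixed.** Section I blames side effects together with contraindications, and Section V links withdrawal to existing conditions such as obesity and hypertension. Contraindications are handled by stratification. No passage claims that LNG-IUS reduces withdrawals.
- **Unlisted events are a minor matter.** Section V attributes "gastrointestinal reaction, insomnia, nervousness, dizziness, coagulation" and other effects to this drug class. Insomnia, nervousness and dizziness are not named in I.2, but that list is introduced as non-exhaustive and adverse events are recorded monthly.
- **Condition 2.3(3) alone would be a poor end point.** It needs both intolerance and a clinician's judgement, so women who leave under 2.3(1) because of side effects would be missed. The liver-function rule applies only to oral-progestogen groups, so stops are not governed alike across arms.

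None of this supplies a severity grade or an analysis of stops. These points narrow the concern and shape the remedy.

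**Conclusion.** The concern holds in limited form. Milder side effects and side-effect withdrawals are both part of the rationale, and neither has a planned analysis; fewer events does. The primary analysis is unaffected, and the correction is a cheap improvement to a secondary end point.

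What the trial could conclude remains limited. Within one cell, power for 25% v 5% stopping is 0.39 or 0.44. Pooling raises it to 0.74, still below the 0.8 used in III.1, and to 0.55 for 20% v 5%. These values assume the stated group sizes are reached, a two-sided 0.05 uncorrected chi-square, and stopping rates that have no source in the documents. The added analyses would make tolerability measurable but could confirm only large differences.

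**What to change.** 1. **New secondary end point (I.2 and III.3).** Add stopping protocol treatment because of side effects, in all randomised women. Count stops under 2.3(3) and stops under 2.3(1) where the recorded reason is a side effect. Show separately the stops under the liver-function rule, because it applies only to oral-progestogen groups.
2. **Comparison.** Compare by arm within each cell. For MPA 500 mg v LNG-IUS alone, also compare across the two cells without contraindications, stratified by cell. Report differences with confidence intervals.
3. **Severity.** Name a grading scale and record a grade for each side effect at the monthly checks in Tables 1 and 2. Compare worst grade by arm with an ordinal test, alongside frequency. Tabulate the full grade distribution as well, because an ordinal test is not always the more sensitive. For none/mild/severe of 30/30/40% v 30/60/10%, simulation gives it about 0.24 power at 20 per arm, against 0.62 for severe v not severe.
4. **Status.** Label these as supportive secondary analyses without multiplicity control.

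The cost is amended wording, one extra form field (with the reason for any voluntary withdrawal noted) and a few more comparisons. No visit, test or treatment changes.

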**3. Study Design**

**3.1 For Patients Having EAH**

The treatment schedule for EAH is summarized in Figure 1 and Table 1.

**Fig. 1** Study design. EAH, atypical endometrial hyperplasia; EC, endometrial cancer; MPA, medroxyprogesterone acetate; QD, once a day; LNG-IUS, Levonorgestrel-Releasing intrauterine system, Mirena®, Bayer Health Care Pharmaceutical Inc., Wayne, NY; GnRH-a, gonadotropin-releasing hormone agonists, Leuporelin acetate microspheres; mo, months; CR, complete response; PR, partial response; NC, no change; PD, progressive disease

**Table 1** The treatment schedule for atypical endometrial hyperplasia

Visits	1st	2nd	3rd	4th	5th	6th	7th	8th	9th	10th	11th	12th
Times	-1	-1/4	0	1	2	3	4	5	6	7	8	9

(month)												
Procedures	Pre-screening	Screening	Treatment Beginning	The 1st cycle			The 2nd cycle			The 3rd cycle (if necessary)		
History collection	√					√			√			√
Physical examination	√	√	√			√			√			√
Weight	√		√	√	√	√	√	√	√	√	√	√
Thinprep cytology test (TCT)	√											
Breast ultrasound	√											
Gynecological ultrasound	√					√			√			√
Endocrine examinations	√											
Liver function test	√			√	√	√	√	√	√	√	√	√
Coagulation function test	√					√			√			√
Pathology examinations	√	√				√			√			√
Hysteroscopy		√				√			√			√
Criteria	√	√				√			√			
Informed consent			√									
Random assignment			√									
Medical treatment			√	√	√	√	√	√	√	√	√	
Response evaluation						√			√			√
Adverse resection				√	√	√	√	√	√	√	√	√
Adverse events			√	√	√	√	√	√	√	√	√	√

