**Comments:**

(1) The basic history collection includes detailed history of prior treatment; with or without contraindications of oral highly active progestogens: hypertension, diabetes (DM), liver function damage, thrombotic disease and so on; with or without reproductive endocrine disease: infertility, PCO syndrome, insulin resistance (IR), impaired fasting glucose (IFG) and so on; with or without any other system disease; surgical history, allergy history; family history especially for carcinomas.

(2) The basic endocrine examinations include sex hormone, anti mullerian hormone (AMH), and insulin release test (IRT) to rule out PCO syndrome, IR, IFG, and DM. Follow-up treatment will be provided when necessary.

(3) If the patients have abnormality in breast ultrasound, she needs to visit the Department of Breast Surgery to evaluate the risk of continuous progesterone treatment.

(4) Based on the inclusion and exclusion criteria of this study, the patients are allocated to one of the arms by central randomization with study site allocation. The arms and interventions and the probability of distribution are as follows:

1) If the patients does not have thromboembolism, liver dysfunction, hypertension, or diabetes, she will be assigned to one of the following two groups, with a probability of 50%, respectively: a) sequential oral medroxyprogesterone acetate (MPA) 500mg QD group; and b) LNG-IUS (Mirena®) group.

2) If the patients are diagnosed of thromboembolism, liver dysfunction, hypertension, or diabetes, she will be assigned to one of the following two groups, with a probability of 50%, respectively: a) intramuscular injection of leuporelin acetate microspheres (GnRH-a) + LNG-IUS group; and b) LNG-IUS (Mirena®) group.

(5) For the groups of oral highly active progestogens, medicine treatment should only be continued if the liver function is normal, which is evaluated by monthly tests.

(6) For the groups of LNG-IUS, the medical device needs to be replaced by a new one on every hysteroscopy to insure adequate drug release

(7) Endometrial tissue sampling for diagnosis should be performed by hysteroscopy every 3 months, and the histologic diagnoses of all specimens are made by two categorized pathologists.

[figure not shown]

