(8) After 6 months' continuous progestogen-based therapy, if the patients has PR/NC, progestogen-based therapy should be continued for one more cycle (3 months), and if the patient still has PR/NC, she will withdraw from this trial and undergo hysterectomy; if the patients has CR at the second or third endometrial evaluation, fertility treatment will be initiated immediately; and if the patients has documented progression on the biopsies at any time, the protocol treatment will be stopped and hysterectomy be recommended.

(9) The option of natural conception or assisted reproduction should be discussed with the fertility specialist in the reproduction center of our hospital; assisted reproduction is recommended if the patients 1) has history of infertility; 2) has risk factors for infertility such as PCO syndrome, obesity, diabetes, and lack of ovulation; or 3) suffers from failed pregnancies after 6 months of natural conception.

- (10) If the patient succeeds in conceiving, she will receive professional prenatal examinations from the obstetrics specialist in our hospital.
- (11) All the professors in the Department of Obstetrics and Reproductive Center of our hospital are on this research team.
- (12) Long-term follow-up will proceed even after treatments are finished, and corresponding clinical treatments will be provided for patients with different conditions.

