(9) For the groups of LNG-IUS, the medical device needs to be replaced by a new one on every hysteroscopy to insure adequate drug release

(10) Endometrial tissue sampling for diagnosis should be carried out by hysteroscopy every 3 months, and histologic diagnoses of all specimens are made by two categorized pathologists.

(11) After 6 months' continuous progestogen-based therapy, if the patient has PR/NC, progestogen-based therapy should be continued for one more cycle (3 months), and if the patient still has PR/NC, she will withdraw from this trial and undergo hysterectomy; if the patient has CR at the second or third endometrial evaluation, fertility treatment will be initiated immediately; and if the patient has documented progression on the biopsies at any time, the protocol treatments will be stopped and hysterectomy be recommended.

(12) The option of natural conception or assisted reproduction should be discussed with the fertility specialist in the reproduction center of our hospital; assisted reproduction is recommended if the patient 1) has history of infertility; 2) has risk factors of infertility such as PCO syndrome, obesity, diabetes, and lack of ovulation; or 3) suffers from failed pregnancies after 6 months of natural conception.

(13) If the patient succeeds in conceiving, she will receive professional prenatal examinations from the obstetrics specialist in our hospital.

(14) All the professors in the Department of Obstetrics and Reproductive Center of our hospital are on this research team.

(15) Long-term follow-up will proceed even after treatments are finished, and corresponding clinical treatments will be provided for patients with different conditions.

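### Kidney dysfunction, glucose intolerance and diabetes are compared between arms without any on-treatment test for them, so the counts cover only clinically recognised cases

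*Combined protocol and SAP*

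**What the plan says.** Section I.2 (Secondary End Points) lists 14 side-effects to be compared. The list ends with "liver dysfunction, kidney dysfunction, glucose intolerance, and diabetes". Section III.3 (Statistics) specifies "chi-square test for secondary end points", so each patient needs a yes/no status for each item.

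The visit schedules are Table 1 (EAH) and Table 2 (EC). Neither has a kidney-function row. The glucose-related test sits in the row "Endocrine examinations", ticked once in each table, at month -1. The comments to both tables say what that row contains and why: sex hormone, AMH and the "insulin release test (IRT) to rule out PCO syndrome, IR, IFG, and DM". That is a baseline rule-out. The same comment promises follow-up treatment where needed, which is not a scheduled repeat test.

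Treatment length varies by patient. Months 7 to 9 fall under a column heading that begins "The 3rd cycle (if necessary". Section 3.1 comment (8) says "if the patients has CR at the second or third endometrial evaluation, fertility treatment will be initiated immediately", and section 3.2 comment (11) says the same for EC. Section 2.3 lets patients leave treatment earlier, for example "If the participants cannot tolerate adverse drug reaction".

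**The concern.** Kidney dysfunction and glucose intolerance are mainly laboratory findings, and early diabetes can be silent. If the schedule does not look for them, a count of zero can mean either that nothing happened or that nobody tested. A reader of the results table cannot tell which.

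The plan does not treat laboratory safety as unimportant: it tests liver function every month. Section V itself names kidney dysfunction among the side-effects of highly active progestogens. An item that the protocol raises as a risk and promises to compare should have a way of being found.

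A second gap concerns diabetes, which is one of the four conditions that place a patient in the contraindication strata. The plan does not say that only new or worsened diabetes counts there as a side-effect.

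At stake is the reading of three secondary safety comparisons, not the efficacy result.

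**Working it through.** **1. Scheduled capture per patient.** Ticks counted across the 12 visit columns; the rows below agree in Tables 1 and 2.

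| Row | Visits ticked | After treatment start |
|---|---|---|
| Kidney function | 0 of 12 (no row) | 0 |
| Endocrine (glucose-related) | 1 of 12 (month -1) | 0 |
| Liver function | 10 of 12 (months -1, 1 to 9) | 9 |
| Coagulation | 4 of 12 (months -1, 3, 6, 9) | 3 |
| History | 4 of 12 (months -1, 3, 6, 9) | 3 |
| Adverse events | 10 of 12 (months 0 to 9) | 9, plus month 0 |

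History and adverse-event recording are the main remaining routes for the three items. Neither has a test or threshold attached.

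**2. The three items are not equally affected.**
- Kidney dysfunction: no baseline value and no follow-up test, so new cases cannot be separated from existing ones either.
- Glucose intolerance: baseline test, no follow-up test.
- Diabetes: baseline rule-out, and history repeated at months 3, 6 and 9. In the strata without contraindications, known diabetics are excluded by allocation, so diabetes recorded later is new. The new-onset question arises only in the contraindication strata, which hold 2×30 + 2×14 = 88 of the planned 3×18 + 2×30 + 2×14 + 2×20 = 182 patients (section III.1).

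**3. What a zero count would exclude.** With every case found, the one-sided 95% upper limit on the true rate is 1 − 0.05^(1/n):
- n = 14: 19.3%
- n = 18: 15.3%
- n = 20: 13.9%
- n = 30: 9.5%

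If only a share s of cases is recognised, the limit becomes that figure divided by s. The documents give no value for s. Assuming s = 0.5 at n = 20, the limit is 13.9%/0.5 = 27.8%; for s = 0.75 to 0.25 it runs from 18.5% to 55.6%.

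**4. Cost in power if cases are missed equally in all arms.** Illustration with assumed true rates of 30% vs 5%, two-sided alpha 0.05, normal approximation (pooled variance under the null, unpooled under the alternative):

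| Per arm | All found | Half found | Quarter found |
|---|---|---|---|
| 14 | 0.41 | 0.21 | 0.12 |
| 18 | 0.51 | 0.26 | 0.15 |
| 20 | 0.55 | 0.28 | 0.16 |
| 30 | 0.73 | 0.40 | 0.22 |

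**5. What full testing could detect.** For k vs 0 events with n per arm, the uncorrected chi-square is 2nk/(2n − k), and the two-sided Fisher p is 2·C(n,k)/C(2n,k).

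| Per arm | Chi-square p, 3 vs 0 | Chi-square p, 4 vs 0 | Fisher p, 4 vs 0 | Fisher p, 5 vs 0 |
|---|---|---|---|---|
| 14 | 0.067 | 0.031 | 0.098 | 0.041 |
| 18 | 0.070 | 0.034 | 0.104 | 0.045 |
| 20 | 0.072 | 0.035 | 0.106 | 0.047 |
| 30 | 0.076 | 0.038 | 0.112 | 0.052 |

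At 30 per arm Fisher needs 6 vs 0 (p = 0.024). The Fisher thresholds are 5/14 = 36%, 5/18 = 28%, 5/20 = 25% and 6/30 = 20% of an arm.

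The EC stratum without contraindications has three arms of 18. For 3 vs 0 vs 0, each arm expects 1 event and 17 non-events. The overall uncorrected chi-square is (4 + 1 + 1)/1 + (4 + 1 + 1)/17 = 6.35 on 2 degrees of freedom, p = 0.042.

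**The case against.** The best reply is that the schedule does have routes for these events. Adverse events are recorded from month 0 to month 9 and history is retaken every three months. The history comment names diabetes and impaired fasting glucose. If under-detection is the same in every arm, the comparison of recognised events keeps its meaning and mainly loses power, as step 4 shows. This stands. A reader might infer that the chi-square comparisons cannot be interpreted at all, but the documents do not support that.

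A reader might also infer biased detection between arms. No blinding is described and tablet, injection and device are easily told apart, so unscheduled testing could differ by arm. Nothing in the documents shows that it would, so this remains a possibility only.

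The protocol's rationale has limits too. Section V ties kidney effects to highly active progestogens, and the contraindication strata have no oral-progestogen arm. The fasting hyperglycemia mentioned in section I may be a comorbidity rather than a drug effect. Even so, the secondary end point makes no exception for any stratum.

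Finally, only three of 14 listed side-effects are involved. Weight and liver damage, the protocol's own examples of better LNG-IUS tolerability, are both covered by monthly measurements. This stands and limits the reach of the point.

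**Conclusion.** The point holds within limits. As scheduled, the three items will be counted as clinically recognised events. Silent on-treatment cases will be missed, and a low or zero count must not be reported as absence of the effect. The gap is complete for kidney dysfunction, substantial for glucose intolerance and smallest for diabetes.

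The conclusion rests on the visit tables and on no assumed rate. The detection shares and the 30% vs 5% rates above only illustrate size. Efficacy conclusions are unaffected. Nor does the point undermine the weight and liver comparisons, as a reader might infer. Testing everyone would make a low count more informative, but at the planned arm sizes it would still reveal only large differences. This is a change the sponsor should make, not one on which the trial depends.

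**What to change.** Choose one.

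**Option 1: measure the items.** Add creatinine and a fasting glucose measure at months -1, 3 and 6, identically in all arms. Liver and coagulation tests are already scheduled at those visits. State a laboratory definition of each outcome in advance. Compare arms through month 6, because the third cycle is given only to patients who need it. Report the number tested per arm, since some patients will stop before month 6. Cost: at most 182 × 3 × 2 = 1,092 routine assays, no new visit, and a fasting requirement that the documents do not now state. If glucose intolerance is meant to cover more than a fasting sample shows, rename it, or repeat the month -1 test at months 3 and 6; that repeat is not in the 1,092 and must be costed separately.

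**Option 2: narrow the claim.** Remove the three items from the compared end points and report them descriptively as clinically recognised adverse events. Cost: wording only, but the trial then makes no comparative statement on kidney or glucose effects.

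**Under either option:** in the contraindication strata, count diabetes only as new onset or worsening from baseline.
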